5.1.2 Expansion (including Safety Run-in) Inclusion Criteria

Each potential subject must fulfill all of the following criteria to be enrolled in the trial.

1. Be at least 18 years of age.
2. Must sign an ICF prior to any screening procedures indicating that they understand the purpose of the trial, the procedures required for the trial, and are willing to participate in the trial prior to any other trial-related assessments or procedures.
3. Has histologically or cytologically confirmed relapsed or refractory B-cell NHL. All subjects must have received at least 2 prior lines of systemic therapy, and,
 - a. For FL and DLBCL, at least 1 of the 2 prior lines of treatment must have been a CD20-containing systemic regimen;
 - b. For CLL, subjects must have received at least one prior line of BTK inhibitor or BCL-2 inhibitor.

Note: See Section 11.8.1.3 for definitions of “relapsed” disease.

4. Has 1 of the following B-cell NHL subtypes for the Expansion (including safety run-in):
 - a. DLBCL, de novo or histologically transformed
 - b. FL Grade 1, 2 and 3a, with advanced symptomatic disease and with a need for treatment initiation
 - c. CLL, must have active disease that needs treatment with at least 1 of the following criteria being met ([Hallek et al., 2018](#)):
 - i. Evidence of progressive marrow failure as manifested by the development of, or worsening of, anemia and/or thrombocytopenia
 - ii. Massive (ie, ≥ 6 cm below the left costal margin) or progressive or symptomatic splenomegaly
 - iii. Massive nodes (ie, ≥ 10 cm in longest diameter) or progressive or symptomatic lymphadenopathy
 - Progressive lymphocytosis with an increase of $\geq 50\%$ over a 2-month period, or LDT < 6 months
 - Autoimmune complications including anemia or thrombocytopenia poorly responsive to corticosteroids
 - Symptomatic or functional extranodal involvement (eg, skin, kidney, lung, spine)
 - Disease-related symptoms as defined by any of the following:
 - Unintentional weight loss $\geq 10\%$ within the previous 6 months

- Significant fatigue
- Fevers $\geq 38.0^{\circ}\text{C}$ (100.5°F) for 2 or more weeks without evidence of infection
- Night sweats for ≥ 1 month without evidence of infection

d. GEN3009 + GEN3013 combination cohort only: Documented CD20+ DLBCL or FL based on representative pathology report

5. Has measurable disease for B-cell NHL:

- a. A FDG-PET CT scan demonstrating positive lesion compatible with CT (or MRI)-defined anatomical tumor sites, and
- b. A CT scan (MRI) with involvement of ≥ 2 clearly demarcated lesions/nodes with long axis >1.5 cm and short axis >1.0 cm or 1 clearly demarcated lesion/node with a long axis >2.0 cm and a short axis ≥ 1.0 cm.

Note: Subjects who do not have FDG-avid lymphoma at screening will be eligible if they meet criterion “5b”.

6. Has measurable disease for CLL with at least one of the following criteria:

- a. $\geq 5 \times 10^9/\text{L}$ ($5,000/\mu\text{L}$) B lymphocytes in peripheral blood
- b. Presence of measurable lymphadenopathy and/or organomegaly

7. Has ECOG performance status of 0 or 1.

8. Has acceptable laboratory parameters as follows:

Parameter	Result
a. Creatinine clearance	$>50 \text{ mL/min}$ (Cockcroft-Gault) or serum creatinine $\leq 1.5 \times \text{ULN}$ (refer to Appendix 1)
b. Serum alanine transaminase (ALT)	$\leq 2.5 \times \text{ULN}$
c. Serum aspartate transaminase (AST)	$\leq 2.5 \times \text{ULN}$
d. Total bilirubin	$\leq 1.5 \times \text{ULN}$ Note: Subjects with Gilbert's syndrome may be included if total bilirubin is $\leq 3 \times \text{ULN}$ and direct bilirubin is $\leq 1.5 \times \text{ULN}$
e. Hemoglobin	$\geq 5.6 \text{ mmol/L}$ (9.0 g/dL) Note: Without transfusion within 7 days of determination of eligibility.
f. Absolute neutrophil count	B-cell NHL : $\geq 1.0 \times 10^9/\text{L}$ ($1,000/\mu\text{L}$) CLL : $\geq 1.0 \times 10^9/\text{L}$ ($1,000/\mu\text{L}$) unless due to bone marrow involvement Note: Without growth factor support within 7 days of determination of eligibility (14 days if pegylated growth factor such as pegfilgrastim).
g. Platelet count	B-cell NHL : $\geq 75 \times 10^9/\text{L}$ ($75,000/\mu\text{L}$) Note: In presence of bone marrow involvement, platelets $\geq 50 \times 10^9/\text{L}$. CLL : $\geq 30 \times 10^9/\text{L}$ ($30,000/\mu\text{L}$)

		Note: Without transfusion within 7 days of determination of eligibility.
h.	Coagulation status: PT/INR/aPTT	Prothrombin time (PT)/International normalized ratio (INR)/Activated partial thromboplastin time (aPTT) $\leq 1.5 \times$ ULN

9. Subjects must have a life expectancy of at least 3 months.
10. A woman of reproductive potential must agree to use adequate contraception during the trial and for 12 months after the last GEN3009 and/or GEN3013 administration. Adequate contraception is defined as highly effective methods of contraception (refer to [Appendix 12](#) for more information). In countries where 2 highly effective methods of contraception are required, both methods will be required for inclusion.
11. A woman of childbearing potential must have a negative serum beta-hCG at screening.
12. A woman must agree not to donate eggs (ova, oocytes) for the purposes of assisted reproduction during the trial and for 12 months after receiving the last dose of GEN3009 and/or GEN3013.
13. A man who is sexually active with a woman of childbearing potential and has not had a vasectomy must agree to use a barrier method of birth control, eg, condom only and with spermicidal foam/gel/film/cream/suppository and partner with occlusive cap (diaphragm or cervical/vault caps) with spermicidal foam/gel/film/cream/suppository, and all men must also not donate sperm during the trial and for 12 months after receiving the last dose of GEN3009 and/or GEN3013.
14. Must be willing and able to adhere to the requirements and restrictions specified in the ICF and this protocol.
15. **Sites in France only:** Must have a social security number or equivalent per local requirements.

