GEN3009 IV as assigned	GEN3013 s.c.								
DL1: CCI mg	DL1: 48 mg								
DL2: RP2D									

Cycles 1-3: Days 1, 8, 15, 22Cycles 4-12: Day 1	
Cycle 1:
0.16 mg (priming dose) on Day 80.8 mg (intermediate dose) on Day 1548 mg (full dose) on Day 22Cycles 2 and 3: 48 mg on Days 1, 8, 15, and 22Cycles 4-12: 48 mg on Day 1 
After completion of Cycle 12:
 
Subjects who are in SD, PR or CR:
Every 4 weeks (Cycles 13, 14, 15+): 48 m								
Population	For GEN3009 monotherapy, approximately 90 subjects with R/R B-cell NHL (including CLL/SLL, will be enrolled in the Dose Escalation). Approximately 92 subjects will be enrolled in the Dose Expansion.								
Key Inclusion Criteria	Each potential subject must fulfill all of the following criteria to be enrolled in the trial (applicable to both Dose Escalation and Dose Expansion unless otherwise indicated). 
Be at least 18 years of age.Must sign an informed consent form (ICF) prior to any screening procedures.Has histologically or cytologically confirmed relapsed or refractory B-cell NHL with no available standard therapy or is not a candidate for available standard therapy, and for whom, in the opinion of the investigator, experimental therapy with GEN3009 or GEN3009 + GEN3013 may be beneficial. All subjects must have received at least 2 prior lines of systemic therapy, and,
For all indolent NHL (FL, marginal zone lymphoma [MZL], and SLL) as well as aggressive NHL (DLBCL, high-grade B-cell lymphoma [HGBCL], and primary mediastinal large B-								

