2.3 Benefit-Risk Assessment

2.3.1 GEN3009 Monotherapy

GCT3009-01 is a FIH trial of GEN3009 in R/R B-cell NHL, and the safety profile for GEN3009 is still being established with limited data collected. However, the benefit-risk profile of GEN3009 appears to be favorable. The trial population is limited to subjects with R/R B-cell NHL who have exhausted standard therapies or are ineligible for standard therapies. The risks to subjects in this trial are being minimized by compliance with the eligibility criteria, trial procedures, with close monitoring, and proper/prompt management of TEAEs.

CD37 is exclusively expressed in hematopoietic lineage cells with a high expression in B cells and a much lower expression on T cells, monocytes, NK cells, and neutrophils. In recent years, several CD37-targeting biologics including otlertuzumab, BI836826, IMGN529, betalutin (¹⁷⁷Lu-conjugated lilotumab), and AGS-67E have been developed and evaluated in Phase 1/2a clinical trials in various B-cell NHL ([Stathis et al., 2018](#)); ([Stilgenbauer et al., 2019](#)); ([Witkowska et al., 2018](#)); ([Blakkisrud et al., 2017](#)); ([Payandeh et al., 2018](#); [Salles, 2019](#)). Findings from these early phase studies indicate manageable safety profiles with majority of adverse reactions being hematological (eg, neutropenia, thrombocytopenia, anemia). IRRs and infections were common TEAEs. Of note, no CRS was reported. Preliminary data showed single-agent activity: betalutin in relapsed indolent B-cell NHL including FL, MCL, and MZL: ORR 69% with 28% being CR ([Kolstad et al., 2017](#)); IMGN529 in R/R B-cell NHL: ORR 13% with 4 responders in DLBCL ([Stathis et al., 2018](#)); BI836826 in R/R CLL: ORR 35% all being PR ([Stilgenbauer et al., 2019](#)). Promising clinical efficacy of otlertuzumab was observed in indolent B-cell NHL when combined with BR ([Gopal et al., 2014b](#)) and in relapsed CLL when combined with bendamustine ([Robak et al., 2017](#)). Collectively, these data warrant clinical development of CD37-targeting compounds for B-cell NHL.

The expected MoA for GEN3009 include: 1) enhanced CDC activity through Fc-Fc-mediated hexamerization upon binding to CD37 on the target cell surface, and 2) Fc_YR-mediated effector functions including ADCC activity and ADCP activity.

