In summary, this trial explores GEN3009 as a single agent and in combination with GEN3013 in subjects with R/R B-cell NHL who have limited treatment options. Based on nonclinical data and preliminary clinical data from GEN3009 and GEN3013 and clinical data from other CD37-targeting compounds, GEN3009 monotherapy and in combination with GEN3013 have the potential to address the highly unmet medical need in this patient population. With safety precautions and close monitoring plan in place, the described risks are outweighed by the potential benefit subjects might receive from GEN3009 alone or in combination with GEN3013.

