5 TRIAL POPULATION(S)

5.1 Inclusion Criteria

5.1.1 Dose Escalation Inclusion Criteria

Each potential subject must fulfill all of the following criteria to be enrolled in the trial.

1. Be at least 18 years of age.
2. Must sign an informed consent form (ICF) prior to any screening procedures indicating that they understand the purpose of the trial, the procedures required for the trial, and are willing to participate in the trial prior to any other trial-related assessments or procedures.
3. Criterion updated as per Amendment 1
 - 3.1 Criterion updated as per Amendment 3
 - 3.2 Criterion updated as per Amendment 5
 - 3.3 Has histologically or cytologically confirmed relapsed or refractory B-cell NHL with no available standard therapy or is not a candidate for available standard therapy, and for whom, in the opinion of the investigator, experimental therapy with GEN3009 may be beneficial. All subjects must have received at least 2 prior lines of systemic therapy, and,
 - a. For all indolent NHL (FL, MZL, and SLL) as well as aggressive NHL (DLBCL, HGBCL, and PMBCL), at least 1 of the 2 prior lines of treatment must have been a CD20-containing systemic regimen;
 - b. For MCL, subjects must have had or are otherwise ineligible for treatment with a BTK inhibitor, and;
 - c. For CLL, subjects must have received at least 1 prior line of BTK inhibitor or BCL-2 inhibitor.
4. Criterion updated as per Amendment 5
 - 4.1 Has 1 of the following B-cell NHL subtypes for the Dose Escalation:
 - a. DLBCL, de novo or histologically transformed
 - b. HGBCL ([Swerdlow et al., 2016](#))
 - c. PMBCL
 - d. FL, with advanced symptomatic disease and with a need for treatment
 - e. MCL, without leukemic manifestation
 - f. MZL, either nodal, extranodal, or mucosa associated, with a need for treatment initiation based on symptoms and/or disease burden
 - g. SLL, with a need for treatment based on symptoms and/or disease burden
 - h. CLL with active disease that needs treatment based on the International Workshop on Chronic Lymphocytic Leukemia [iwCLL] criteria) ([Hallek et al., 2018](#))
 - i. Criterion updated as per Amendment 3

5. Criterion removed as per Amendment 5
6. Criterion updated as per Amendment 5

6.1 Has measurable disease:

i. B-cell NHL:

- a. A fluorodeoxyglucose (FDG)-positron emission tomography (PET) computed tomography (CT) scan demonstrating positive lesion compatible with CT (or magnetic resonance imaging [MRI])-defined anatomical tumor sites

and

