5.3 Screen Failures

Screen failures are defined as subjects who consent to participate in the clinical trial but do not meet the protocol-defined eligibility criteria (refer to Section 5.1 and 5.2). Minimal information to be documented includes demography, reason for screening failure (eg, eligibility criteria not met, subject withdrew consent, other reasons) and any SAEs or AEs related to a trial assessment.

Individuals who do not meet the criteria for participation in this trial (screen failures) may be rescreened. The rescreening must be approved by the sponsor to ensure that the safety of the subject is not compromised. Screen failures may be rescreened only once. Subjects are required to sign a new ICF if updates have been made since signing the most recent ICF. All eligibility criteria must be re-assessed at the rescreening visit.

Previously submitted tumor biopsy samples are acceptable if obtained within 6 months prior to Cycle 1 Day 1. The following screening assessments may be used for rescreening if performed ≤ 3 weeks prior to Cycle 1 Day 1 or if approved by sponsor:

- Previously submitted FDG-PET CT, CT, or MRI scans with acquisition date ≤ 3 weeks prior to Cycle 1 Day 1. Scans that exceed the 3-week window may be used for trial enrollment with sponsor's approval.
- Screening laboratory assessments with the protocol-defined timelines as indicated in the visit assessment schedules (refer to [Table 2](#) and [Table 5](#)).

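### The Expansion inclusion criteria (5.1.2) omit the standard-therapy limit that the Synopsis applies to both parts and that Section 2.3.1 states as a fact about the trial population

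*Protocol*

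**What the plan says.** Section 5.1.2, the inclusion list for the Expansion and its safety run-in, opens criterion 3 with: "Has histologically or cytologically confirmed relapsed or refractory B-cell NHL. All subjects must have received at least 2 prior lines of systemic therapy". It then asks for a CD20-containing regimen among the prior lines for FL and DLBCL, and a BTK or BCL-2 inhibitor for CLL. It says nothing about whether a standard therapy is still open to the patient.

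The Synopsis heads its key inclusion criteria as "applicable to both Dose Escalation and Dose Expansion unless otherwise indicated". Its disease criterion requires "relapsed or refractory B-cell NHL with no available standard therapy or is not a candidate for available standard therapy", and the sentence ends with "available standard therapy, and for whom, in the opinion of the investigator, experimental therapy with GEN3009 or GEN3009 + GEN3013 may be beneficial".

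Section 5.1.1 criterion 3.3, for Dose Escalation, keeps the same limit. The patient either has no standard therapy available or "is not a candidate for available standard therapy, and for whom, in the opinion of the investigator, experimental therapy with GEN3009 may be beneficial".

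Section 2.3.1, in the benefit-risk assessment for monotherapy, says: "The trial population is limited to subjects with R/R B-cell NHL who have exhausted standard therapies or are ineligible for standard therapies". The closing summary of Section 2.3.2 is weaker. It describes GEN3009 alone and "in combination with GEN3013 in subjects with R/R B-cell NHL who have limited treatment options".

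Section 5.3 defines screen failures as consenting subjects who "do not meet the protocol-defined eligibility criteria (refer to Section 5.1 and 5.2").

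**The concern.** The Synopsis and Section 2.3.1 tell an ethics committee or a site that patients with a usable standard therapy will not be enrolled. The list that a site applies at screening for the Expansion contains no such rule. These statements cannot all describe the same trial.

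What is at stake is subject protection. Section 2.3.1 calls the safety profile of GEN3009 still under establishment, with limited data, and sets the population limit beside that statement as part of the benefit-risk argument. At the June 2021 data cut in Section 2.1.4.1, 18 subjects had been evaluated for dose-limiting toxicity. If the limit is not in the operative criteria, an Expansion subject could receive a first-in-human antibody, alone or with GEN3013, without anyone having been required to ask whether a standard option remained. Criterion 3 also drops the companion requirement that the investigator consider the experimental therapy potentially beneficial.

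**Working it through.** The protocol gives no figure to reproduce here. The check is a comparison of the current texts.

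| Place | Covers | Standard-therapy limit |
|---|---|---|
| Synopsis, Key Inclusion Criteria | Both parts unless marked otherwise; the clause names the combination | Present, unmarked |
| 5.1.1 criterion 3.3 | Dose Escalation | Present |
| 5.1.2 criterion 3 | Expansion and safety run-in | Absent |
| 2.3.1 | The trial population, under the monotherapy heading | Asserted as fact |
| 2.3.2, closing summary | Monotherapy and combination | Weaker: few options, not none |
| Synopsis rationale and 2.2 | Combination | Described as an option for patients whose standard of care is used up |

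1. *Which list governs?* Section 5.3 points to Sections 5.1 and 5.2. For the Expansion that means 5.1.2 and 5.2.2, not the Synopsis.

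2. *Is the limit restored elsewhere in those lists?* No. The remaining inclusion items in 5.1.2 cover histology, measurable disease, performance status, laboratory values, life expectancy, contraception and consent. In 5.2.2 the nearest item is exclusion 25. It turns on whether the subject has a condition that, in the investigator's opinion, makes participation contrary to the subject's interest or would confound assessments. It does not ask whether a standard therapy remains.

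3. *Do the prior-therapy rules amount to the same limit?* No. Two prior lines, including a named class, describe what a patient has had. The Synopsis and 5.1.1 impose rules of this kind as well as the standard-therapy limit, so the protocol itself treats the two as separate requirements.

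4. *Was the Synopsis clause meant for Dose Escalation alone?* Its wording says otherwise. It covers treatment with GEN3009 + GEN3013, and that combination is given only in the Expansion. The corresponding sentence in 5.1.1 names GEN3009 alone.

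5. *Is a wider Expansion population explained anywhere?* Sections 4.1.2 and 4.2 describe the Expansion cohorts and give no reason for one. The Synopsis rationale and Section 2.2 place the combination with patients who have used up standard of care, which points the other way.

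**The case against.** The best case against the point is that the difference is deliberate, or that the Synopsis is too loose to show otherwise.

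The Synopsis is a merged summary. The same criterion carries prior-therapy rules for mantle cell, marginal zone and other subtypes without marking them as Dose Escalation only, although the subtype list marks those diagnoses that way. So an unmarked item in the Synopsis does not prove that it applies to both parts. That stands as far as it goes. The inference here rests instead on the clause naming the combination.

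Amendment 5 separated the criteria by part, giving as reasons an appropriate population and commitments to health authorities. Expansion subjects enter after the recommended dose is set, and the combination uses only GEN3009 levels already cleared. A wider Expansion population would therefore be a defensible choice. But the protocol nowhere states that choice, and making it would leave the Synopsis and Section 2.3.1 wrong. The documents do not show whether the omission was intended.

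Section 2.3.1 sits under the monotherapy heading, and the 2.3.2 summary is compatible with 5.1.2. Both observations are right. For the three monotherapy cohorts the conflict with 2.3.1 is direct. For the combination it is with the Synopsis, and with 2.3.1 only through its general wording.

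Three stronger readings are tempting and are not supported:

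- A reader might infer that particular patients with a standard option left would be enrolled, for example a DLBCL patient not yet given CAR T therapy or a CLL patient not yet given venetoclax plus rituximab. Sections 2.1.1.1 and 2.1.1.3 describe these treatments but do not call either one standard or available therapy. Section 2.1.1.1 stresses limited access to CAR T, and Section 2.1.1.3 does not report the venetoclax results as obtained after a BTK inhibitor.
- A reader might take the planned Expansion size, approximately 92 in Section 4.1, as the number at stake. That counts everyone screened in under the criterion, not those with a remaining option.
- A reader might infer a bias in response rates. Nothing in the documents gives its direction or size.

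**Conclusion.** The point holds as an internal contradiction in eligibility. Section 5.1.2 criterion 3 is operative for the Expansion and lacks a limit that the Synopsis applies to both parts, 5.1.1 retains and 2.3.1 asserts. The prior-therapy rules and exclusion 25 narrow the gap without closing it.

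The textual mismatch is certain. That the Synopsis clause was meant to reach the Expansion is an inference, though a well-supported one. The conclusion assumes that sites apply Section 5 as written, as Section 5.3 directs. The number of subjects affected cannot be estimated, because the documents do not say how many patients meeting 5.1.2 would still have a standard therapy open to them. No consequence for the objective response rate or complete response rate is claimed. The matter should be corrected because it concerns who may be exposed in a first-in-human trial and the remedy is small.

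**What to change.** In Section 5.1.2 criterion 3, after the words on relapsed or refractory B-cell NHL, insert the Synopsis limit in full: the clause that begins within "relapsed or refractory B-cell NHL with no available standard therapy or is not a candidate for available standard therapy" and continues to the end of "available standard therapy, and for whom, in the opinion of the investigator, experimental therapy with GEN3009 or GEN3009 + GEN3013 may be beneficial" (the two quotations overlap at the mention of available standard therapy). This restores both the standard-therapy condition and the investigator's judgement of possible benefit, in wording that already covers the combination.

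If the sponsor intended a wider Expansion population, mark the Synopsis clause as applying to Dose Escalation only, remove the combination from it, and correct the population statement in Section 2.3.1 so that the benefit-risk argument describes the patients who will be enrolled.

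The first route costs one clause in a protocol amendment, with the ethics committee approval that Sections 13.2.2 and 14.1 require, and possibly slower Expansion accrual. The documents give no basis for estimating how much slower. The second route also needs an amendment but leaves the entry criteria in Section 5 as they are.
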